### **2.2.2. Long-term Use Surveillance**

*The objective of this study is to assess the safety of the long-term use of TORISEL 25 mg Injection (hereinafter called this drug) particularly for the onset of interstitial lung disease from Weeks 25 to 96 after the start of administration.*

## **3. INTERIM AND FINAL ANALYSES**

Interim analyses for periodic safety update reports will be periodically performed in this study. Among statistical analyses specified in this plan, only those necessary for periodic safety update reports will be performed at interim analyses. In addition, the final analysis for application for reexamination will be performed. All analyses specified in this plan will be performed at the final analysis.

## **4. HYPOTHESIS AND DECISION RULES**

Because this study is not a confirmatory study, tests are **CCI**. Unless otherwise specified, tests are 2-sided and the significance level is 5%. Two-sided confidence interval will be used in interval estimation, and the confidence coefficient is 95%.

## **5. ANALYSIS SETS**

### **5.1. Safety Analysis Set**

The safety analysis set basically consists of patients who received at least 1 dose of this drug.

However, patients who violate safety criteria among separately specified patient inclusion criteria will be excluded.

Contract deficiency, contract violation, registration violation, no visit after the date of initial dose, no administration, safety evaluation “unassessable”

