1 OBJECTIVES

The objective of this study is to assess the following subject matters in patients treated with TORISEL 25 mg Injection (hereinafter called this drug) in post-marketing actual use conditions, thereby providing proper-use information.

- (1) To confirm the effectiveness and safety of this drug under actual use conditions
- (2) To examine the onset state of adverse events and potentially influencing factors (particularly, major investigation items)
- (3) To examine the onset state and potential onset risk factors of interstitial lung disease

[Conditions for approval]

A drug use investigation must be conducted with all the patients treated with this drug until the data from a specified number of cases are accumulated after the marketing of this drug in order to understand the background information on patients treated with this drug, collect the data on the safety and effectiveness of this drug as early as possible, and take necessary measures to ensure the proper-use of this drug.

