4. To avoid infusion reactions, an antihistamine (e.g., d-chlorpheniramine maleate, diphenhydramine hydrochloride, etc.) should be administered prior to the administration of TORISEL. If infusion reactions occur, stop administration immediately.
5. When administering TORISEL, do not use infusion kits containing DEHP [di-(2-ethylhexyl) phthalate] as a plasticizer.
6. An in-line filter with a pore size of not greater than 5 μm should be used for TORISEL infusion.
7. Dose reduction should be considered for patients with severe hepatic function disorder.

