5.3 Patient registration

(1) Registration procedure

The investigator will complete the registration form on patients treated with this drug provided by sponsor, and submit the form to Patient Registration Center via FAX at treatment.

[TORISEL Patient Registration Center]

[contact] (available 24 hours)

Business hours: 9:00 to 18:00*

(except for Saturdays, Sundays, National Holidays, and New Year Holidays)

*FAX transmission after 17:30 will be responded by 9:30 on the following business day.

(2) Case registration

After the patient was registered, "the announcement of the patient registration" will be sent to the investigator by FAX. Investigator will save the announcement in the site.

If there is something to be confirmed found in the registration form, confirmation will be requested with the investigator. In the case of confirmation, "request form of confirmation" and "registration form (copy)" will be sent from the Registration Center to the investigator by FAX.

(3) Confirmation of registered case

At the end of the registration period, each investigator will confirm that all his/her cases treated with this drug are listed in the "TORISEL Special Investigation Registration List," and submit it to MR in charge with his/her signature or print of his/her name with his/her seal.

When an investigator finds a case treated with the drug, but not registered in the list, the investigator will readily register the case.

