7 STATISTICAL ANALYSIS PLAN

7.1 Analysis Set

As a rule, the safety analysis set will include patients who satisfy the eligibility criteria and confirmed to be treated with this drug at least once. As a rule, the effectiveness analysis set will include patients who are evaluable for effectiveness (patients considered to have received appropriate evaluation). The details of the analysis sets will be specified in a statistical analysis plan.

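### SAP 5.1 drops treated patients who have no visit after the first dose, even when a reaction or death is already recorded, and no planned table gives all-treated incidence of adverse events or deaths

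*SAP*

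**What the plan says.** SAP 5.1 opens broadly: "The safety analysis set basically consists of patients who received at least 1 dose of this drug". It then narrows the set: "patients who violate safety criteria among separately specified patient inclusion criteria will be excluded". The grounds listed are problems with the site contract, "registration violation, no visit after the date of initial dose, no administration", and a safety evaluation rated unassessable. The no-later-visit ground and the unassessable ground thus stand side by side as separate reasons. Neither is defined further in the SAP, which leaves the criteria to a separate specification.

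Protocol 7.1 asks for eligible patients "confirmed to be treated with this drug at least once", as a rule, and leaves the details to the SAP. It does not mention a return visit. The approval condition in Protocol 1 reads: "A drug use investigation must be conducted with all the patients treated with this drug".

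Protocol 7.2.1 places the safety analyses in the safety set. SAP 8.2.2 and 8.2.3 restrict Appendix Forms 2 and 10 to patients included in the safety analysis. SAP 5.3 provides no other analysis set.

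**The concern.** A patient about whom nothing is known after dosing can already be removed as unassessable. What the no-later-visit ground adds is therefore mainly patients whose safety can be assessed: someone who reacts during the first infusion and does not come back, or someone who dies before any further visit.

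The protocol can capture both without a return visit. Section 6.8 has serious events phoned in within 24 hours. Section 6.7 records death as a discontinuation reason and requires an adverse event entry for it. Section 5.4 keeps events in scope for 28 days after stopping. Section 3 says that forms will be collected from early discontinuers to evaluate safety and effectiveness.

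The exclusion may also be related to outcome. Hypersensitivity is a major investigation item (Protocol 6.9), and the precautions in Protocol 2 say: "If infusion reactions occur, stop administration immediately". A reaction can therefore end treatment at dose 1, and failing to return is plausibly more common after a severe reaction, rapid deterioration or death. What is at stake is the incidence of early events in the overall, Grade 3 or higher and major-item tables, the cumulative-incidence graphs, and Appendix Forms 2 and 10. This is a surveillance whose stated purpose is to cover everyone treated.

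**Working it through.** **1. The plan's own figures reproduce.** Inputs from Protocol 3: true incidence 1.0%, 300 cases, at least 95% probability of seeing one event, 50% discontinuation at 12 weeks.
- P(at least 1 event) = 1 − 0.99^300 = 0.951. The smallest sufficient n is 299.
- P(at least 40 interstitial lung disease cases), with n = 300 and rate 17.1%, is 0.968 (exact binomial).
- 300 / (1 − 0.5) = 600 registered.

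**2. Detection is not the problem.** The 300 patients treated for 12 weeks or longer have, by definition, come back after the first dose, so this ground cannot remove them. In the full cohort, removing 5% of 600 leaves 570, and 1 − 0.99^570 = 0.997.

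**3. Incidence can be affected.** Let m be the number excluded out of 600, p the event rate in the safety set, and q the rate among those excluded. Then

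all-treated rate = [p × (600 − m) + q × m] / 600.

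The documents give neither m nor q; the values below are assumptions. For p = 1.0% and m = 12 (2%), the retained patients contribute 0.01 × 588 = 5.88 events:
- q = 10%: (5.88 + 1.2) / 600 = 1.18%
- q = 20%: (5.88 + 2.4) / 600 = 1.38%
- q = 50%: (5.88 + 6.0) / 600 = 1.98%

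The reported 1.0% is then between 0.85 and 0.51 of the all-treated rate. Over a wider range of m:

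| Excluded | q = 1% | q = 10% | q = 20% | q = 50% |
|---|---|---|---|---|
| 6 (1%) | 1.00% | 1.09% | 1.19% | 1.49% |
| 12 (2%) | 1.00% | 1.18% | 1.38% | 1.98% |
| 30 (5%) | 1.00% | 1.45% | 1.95% | 3.45% |

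For a commoner event, p = 5.0% with m = 12, the all-treated rate is 5.1%, 5.3% and 5.9% for q = 10%, 20% and 50%. With q = p there is no bias, and with q below p the direction reverses.

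**4. What the plan already shows about excluded patients.**
- SAP 8.2.4 counts exclusions by reason and lists each excluded patient with the reason.
- SAP 8.2.6 tabulates adverse reactions by inclusion in or exclusion from the safety set, among patients with a collected form. It does not do this for adverse events judged unrelated, or for deaths judged unrelated.
- SAP 9 lists adverse events, serious adverse events, and deaths with and without causality ruled out. The population of these lists is not stated, and they are listings, not incidences.

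No planned table gives the incidence of adverse events, serious adverse events or deaths in all treated patients.

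**The case against.** The strongest reply is that little is hidden. A first-infusion reaction judged drug-related and recorded on the form appears in the inclusion/exclusion table of SAP 8.2.6, the patient is listed with the reason for exclusion, and the listings in SAP 9 may cover deaths. This stands: a reader who infers that these events disappear from the report goes too far. It does not restore them to the main incidences, and it leaves out unrelated events.

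Second, the ground is narrow. Any later visit, scheduled or not, keeps the patient in. The 28-day observation and the tumour evaluation at discontinuation mean that a patient stopped after one infusion is meant to be followed. How the term applies to inpatients is not stated, and the separate criteria may qualify it. This also stands, and it limits how many patients are affected.

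Third, Protocol 7.1 delegates the details to the SAP, so the two documents do not contradict each other. Agreed.

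Two stronger readings are tempting. A reader might infer that cases found late at the list check are removed as registration violations. The documents do not say so, and Protocol 5.3 points the other way: "When an investigator finds a case treated with the drug, but not registered in the list, the investigator will readily register the case". A reader might also put a firm size on the loss: 600 × 1.0% = 6 expected events, and losing 1 to 3 of them gives 5/599 = 0.83% to 3/597 = 0.50%. Nothing in the documents supports that share of losses, and the 1.0% is a planning floor across the major items, not a rate of first-infusion reactions.

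**Conclusion.** The point holds as a possible, outcome-related understatement of early-event incidence, caused by a stated rule that the unassessable ground makes largely unnecessary. Its size is unknown. The 1.18% to 1.98% against 1.0% is an illustration that rests on an assumed 2% excluded and an assumed 10% to 50% event rate among them. The conclusion depends on a literal reading of SAP 5.1 and on no-return patients having more early events than the rest; without the latter there is no downward bias. The existing tables and listings mitigate it in part. The detection target is not threatened. The change is worth making because it is cheap and the outputs concerned are the study's main safety results.

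**What to change.** Preferred: delete the no-later-visit item from the exclusions in SAP 5.1 and align the separately specified criteria. No patient with a confirmed dose and a collected form would then be dropped merely for not returning, whether or not an event was reported. State also that a missing return visit does not by itself make the safety evaluation unassessable. Otherwise patients with nothing reported would leave by that route while those with events stay.

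For the same reason, avoid an edit that keeps no-return patients only when something was reported. Inclusion would then depend on the outcome and could bias incidence upward.

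At minimum: keep the current set and add to SAP 8.2.6 a sensitivity table in all treated patients with a collected form, covering adverse reactions, adverse events, serious adverse events, deaths and the major investigation items. Extend the existing inclusion/exclusion table from adverse reactions to all adverse events and deaths.

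Cost: a short wording change in the SAP and in the separate criteria, or one added table and one extended table. No new data are needed. The downside is that a few patients with very short observation enter the denominator.

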## **5.2. Efficacy Analysis Set**

The efficacy analysis set basically consists of evaluable patients (patients considered to have undergone an appropriate evaluation).

However, patients who violate efficacy criteria among separately specified patient inclusion criteria will be excluded.

Not meeting conditions for target patients, experience of treatment with this drug, efficacy evaluation “unassessable” (not meeting conditions for assessment).

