2 PATIENTS

This study will be conducted with all patients treated with this drug in a specific period of time. The indications and dosage and administration of this drug are described below.

[Indications]

Metastatic and/or unresectable renal cell carcinoma

[Precautions Regarding Indications]

1. The efficacy and safety of TORISEL as postoperative adjuvant chemotherapy has not been established.
2. The selection of patients in whom to administer TORISEL must be performed after thorough consideration of the efficacy and safety data based on understanding of information detailed in "Clinical Studies*".

* Refer to the [Clinical Studies] section in the package insert.

[Dosage and Administration]

The usual adult dosage is temsirolimus 25 mg once weekly, to be administered via intravenous infusion over 30 - 60 minutes. The dosage is to be appropriately reduced according to patient's condition.

[Precautions regarding dosage and administration]

1. The efficacy and safety of TORISEL in combination use with other anti-malignant tumor agents including cytokine preparations have not been established.
2. When interstitial lung disease occurs, interrupt/discontinue administration depending on the symptoms and severity with consideration of the following criteria:

Criteria for interruption or discontinuation in case of interstitial lung disease

| Symptom | Intervention |
|---|--|
| Asymptomatic. Only abnormal imaging findings are observed. | Continue to administer. |
| Mild clinical symptoms ^{Note)} (not interfering activity of daily living) | Interrupt administration until the symptoms recovered. |
| Severe clinical symptoms ^{Note)} (interfering with activity of daily living and need oxygen therapy) | Discontinue |
| Aggravation of clinical symptoms and pulmonary diffusing capacity decreased | |
| Underlying pulmonary disease, with changes in clinical or image findings are observed | |

Note: Dyspnea, cough, etc.

3. If severe adverse reactions (Grade 3 or severer) occur other than interstitial lung disease, interrupt administration of TORISEL until resolution of the adverse reaction. If the adverse reaction is resolved within 3 weeks, administration can be resumed at a reduced dose by one level (reduction levels should proceed as follows: initial dose 25 mg -> 20 mg-> 15 mg -> 10 mg).

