The progress of the target malignant tumor will not be recorded as an adverse event. However, any malignant tumor that reaches a lethal outcome during the observation period has to be recorded as an adverse event. When a patient starts a new treatment, the reportable period of the event will end when the new treatment is started.

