- Platelet count  $\geq 100 \times 10^9/L$  ( $10 \times 10^4/\text{mm}^3$ ) [yes, no];
- Serum creatinine  $\leq 1.5$ -fold of institutional upper reference limit [yes, no];
- BUN  $\leq 1.5$ -fold of institutional upper reference limit [yes, no];
- Total bilirubin  $\leq 1.5$ -fold of institutional upper reference limit [yes, no];
- AST/ALT  $\leq 3$ -fold of institutional upper reference limit ( $\leq 5$ -fold of institutional upper reference limit if liver metastasis is observed) [yes, no];
- Chest CT normal [yes, no];
- Chest X-ray normal [yes, no];
- Measurement of markers for interstitial lung disease such as KL-6, normal [yes, no];
- Pulmonary function test (PFT) normal [yes, no];
- Measurement of oxygen saturation normal [yes, no];
- Total cholesterol  $\leq 350 \text{ mg/dL}$  ( $9.9 \text{ mmol/L}$ ) [yes, no];
- Triglyceride  $\leq 400 \text{ mg/dL}$  ( $4.56 \text{ mmol/L}$ ) [yes, no];
- Hemoglobin A1C  $< 10\%$  [yes, no];

- Fasting blood glucose  $\leq$ 1.5-fold of institutional upper reference limit [yes, no].

[Concomitant therapies and other background information]:

- Concomitant therapy (drug therapy) [absent, present];
- Concomitant therapy (non-drug therapy) [absent, present];
- History of smoking [absent, present];
- Family history of diabetes mellitus [absent, present];
- History of pulmonary surgery [absent, present];
- History of steroid use [absent, present];
- History of occupational and environmental exposure to asbestos, pneumoconiosis-producing dusts, etc. [absent, present];
- History of administration of highly concentrated oxygen for treatment of respiratory disease [absent, present];
- Drug allergies [absent, present];
- Allergies other than drug allergies [absent, present].

Corporate reference value

Test parameter	Unit	Lower limit		Upper limit	
		Male	Female	Male	Female
Hemoglobin	g/dL	13.5	11.3	17.6	15.2
White blood cell count	/ $\mu$ L	3900	3500	9800	9100
White blood cell differential/neutrophil	%	27	28	87	90
Platelet count	$\times 10^4/\mu$ L	13.1	13	36.2	36.9
AST	IU/L	7		38	

Test parameter	Unit	Lower limit		Upper limit	
		Male	Female	Male	Female
ALT	IU/L	4		44	
Total bilirubin	mg/dL	0.2		1	
Total cholesterol	mg/dL	130		219	
Triglyceride	mg/dL	30		150	
Fasting blood glucose	Mg/dL	60		110	
HbA1C	%	4.3		5.8	
BUN	mg/dL	8		20	
Serum creatinine	mg/dL	0.8	0.6	1.2	0.9
K	mEq/L	3.7		4.8	
P	mg/dL	2.5		4.5	
	mmol/L	0.8		1.4	
CRP	mg/dL			0.3	
SpO2	%	95		100	
KL-6	U/mL			500	
SP-D	ng/mL			<110	
SP-A	ng/mL	15		34.2	

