### 8.2.7. Efficacy Analysis

- **Response rate and clinical benefit rate**

The number and percentage of patients by best overall response, the response rate and its 95% confidence interval, and the clinical benefit rate and its 95% confidence interval will be tabulated in the safety analysis set and efficacy analysis set.

The response rate is defined as the percentage of patients whose best overall response is CR or PR.

The clinical benefit rate is defined as the percentage of patients whose best overall response is CR, PR, or SD.

The best overall response is defined as the best response among recorded overall response.

Table 1 of “New Guideline for the Assessment of Treatment Effect on Solid Cancer (Response Evaluation Criteria in Solid Tumors [RECIST] Guideline)–Japan Clinical Oncology Group [JCOG] version in Japanese” will be used for overall response, but overall response based on combinations of tumor response not corresponding to the table because of unknown data and no entry of data was uniquely defined. Therefore, the

tabulation analysis is not in complete compliance with the guideline and uses the guideline for reference.

**Table 1. Overall Response Based on Combinations of Tumor Response in Target and Non-target Lesions Including the Presence or Absence of New Lesions**

Target lesion	Non-target lesion	New lesion	Overall response
HCR	CR	Absent	CR
CR	IR/SD	Absent	PR
PR	Other than PD	Absent	PR
SD	Other than PD	Absent	SD
PD	Any response	Any response	PD
Any response	PD	Any response	PD
Any response	Any response	Present	PD

The following tumor response will be converted as shown by the arrow.

Non-target lesion: Absent → CR, not entered → IR/SD.

New lesion: Not entered → absent.

Overall response not corresponding to any combination in Table 1 after the above conversion will be considered as “unassessable.”

In addition, tabulation will be performed in the same manner by category shown below.

For items using reference laboratory test values, results using corporate reference values will be tabulated separately from results using institutional reference values as necessary.

- Site of metastasis [none, lung, liver, bone, lung + 1 organ, lung + 2 organs, lung +  $\geq 3$  organs,  $\geq 2$  organs other than lung, others];
- Whether criteria for proper use are met [yes, no];

- Prior treatment history [IFN- $\alpha$ , IL-2, Sutent, Nexavar, Afinitor, others];

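### Best overall response has no visible cut-off at other anticancer treatment, so responses recorded under a concurrent anticancer drug count toward this drug's response and clinical benefit rates

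*SAP*

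**What the plan says.** **Who is analysed.** SAP 5.2 opens with a general rule: "The efficacy analysis set basically consists of evaluable patients (patients considered to have undergone an appropriate evaluation"). It then lists the exclusions: "Not meeting conditions for target patients, experience of treatment with this drug, efficacy evaluation “unassessable” (not meeting conditions for assessment"). None of the three concerns other anticancer treatment.

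**How response is scored.** SAP 8.2.7 states: "The best overall response is defined as the best response among recorded overall response". The term unassessable is tied to lesion combinations, not to treatment received: "Overall response not corresponding to any combination in Table 1 after the above conversion will be considered as “unassessable". The same scoring serves both analysis sets, since the response rate and the "clinical benefit rate and its 95% confidence interval will be tabulated in the safety analysis set and efficacy analysis set".

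**Other anticancer treatment.** Protocol section 2 carries a labelling precaution that efficacy and safety "in combination use with other anti-malignant tumor agents including cytokine preparations have not been established". The visible text does not make such use a bar to registration or analysis. Protocol 6.3.1 and 6.3.2 record every concomitant drug and non-drug therapy with its name, period and reason.

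**A rule triggered by new treatment.** The only visible one is in Protocol 6.8 and concerns adverse events: "the reportable period of the event will end when the new treatment is started".

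**The concern.** Response rate and clinical benefit rate are the main effectiveness items in Protocol 7.2.2, and the results go into the re-examination application. There is no control group, so a response helped by another anticancer drug, radiotherapy or surgery cannot be separated from this drug's effect by comparison. If such responses are scored in the ordinary way, the reported rates describe this drug together with whatever else was given. A reader of the tables would have no means of judging how much.

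**Working it through.** **1. The plan's own figures.** The documents state no expected response rate, so there is no effectiveness figure to reproduce. The stated study size does reproduce:
- P(at least 1 event | n = 300, incidence 1.0%) = 1 − 0.99^300 = 0.951
- P(at least 40 interstitial lung disease cases | n = 300, incidence 17.1%) = 0.968
- 300 / (1 − 0.50) = 600 registered

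The point does not depend on these.

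**2. Following one patient through the rules.** Take a patient who receives another systemic anticancer drug alongside this one and is scored PR at Week 16.
- SAP 5.2: the patient has the target disease, no previous use of this drug, and an assessable lesion combination. The patient stays in the efficacy set.
- SAP 8.2.7: PR is a recorded overall response, so best overall response is at least PR. The patient counts in the response rate.
- Safety analysis set: the same best overall response applies, and the efficacy exclusions do not.
- PFS (SAP 6.2): no censoring at the start of other anticancer treatment is stated, so PFS does not offer a corrected view.

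**3. Direction.** Best overall response is a maximum over evaluations. Adding evaluations made under other treatment can leave a patient's value unchanged or improve it, never worsen it. With the denominator held fixed, the rates can only stay the same or rise.

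**4. What the planned tables show.**

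| Planned output | What it gives | What it lacks |
|---|---|---|
| Concomitant medications and non-drug therapies (SAP 8.2.5) | Number and percentage of patients by each drug or therapy, safety set | Any link to response or to evaluation dates |
| Response by the item "Concomitant therapy (drug therapy) [absent, present"] (SAP 8.2.7 with 10.1.1) | Response split by any concomitant drug | Anticancer drugs are not separated; Protocol section 2 calls for antihistamine premedication, so most patients would fall under present |
| Response by non-drug therapy, absent or present (SAP 8.2.7 with 10.1.1) | A partial view of radiotherapy and surgery | Type of therapy, and timing against the evaluation |

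No visible table gives response according to concurrent anticancer drug use or its timing.

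**5. Illustration of size (all inputs assumed).** Let b be the rate on this drug alone, f the share of patients with an evaluation under other anticancer treatment, and q the share of their non-responders who respond to that treatment. Then the reported rate = b + f × (1 − b) × q. With N = 600 (the registration target; the efficacy set would be smaller) and exact 95% intervals:

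| b | f | q | Reported rate | Count | 95% CI |
|---|---|---|---|---|---|
| 5% | 0 | – | 5.0% | 30/600 | 3.4% to 7.1% |
| 5% | 5% | 10% | 0.05 + 0.05 × 0.95 × 0.10 = 5.5% | 33/600 | 3.8% to 7.6% |
| 5% | 20% | 30% | 0.05 + 0.20 × 0.95 × 0.30 = 10.7% | 64/600 | 8.3% to 13.4% |
| 10% | 0 | – | 10.0% | 60/600 | 7.7% to 12.7% |
| 10% | 5% | 10% | 0.10 + 0.05 × 0.90 × 0.10 = 10.5% | 63/600 | 8.2% to 13.2% |
| 10% | 20% | 30% | 0.10 + 0.20 × 0.90 × 0.30 = 15.4% | 92/600 = 15.3% | 12.5% to 18.5% |

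At the low end the shift is about half a percentage point and disappears within the interval. At the high end it doubles a 5% rate.

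**The case against.** **The objective is effectiveness in actual use.** Protocol section 1 says so, and SAP section 4 says the study is not confirmatory. An all-comers rate answers that question. This stands, and it is why the all-comers rate should remain. It does not remove the need to know how much of the rate arose under other anticancer treatment.

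**The rule may exist elsewhere.** SAP 5.2 refers to separately specified inclusion criteria and to conditions for assessment that are not in the public documents, and parts of the SAP's efficacy section are removed or redacted. This also stands. The point is limited to the visible text.

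**The next-treatment route is narrow.** A reader might infer that responses to whatever follows this drug are generally credited to it. Protocol 5.4 and section 6 do not support that. For discontinued cases the last scheduled tumour evaluation is at discontinuation, and only if none was done in the preceding 4 weeks. What remains is that nothing requires that evaluation to precede the next treatment, and any later recorded evaluation would count. For the same reason the contrast with the adverse-event rule in Protocol 6.8 is weaker than it looks: adverse events are followed for 28 days after discontinuation, so they have more need of a cut-off.

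**Other treatment is not hidden.** A reader might infer that its extent appears in no planned table. It does appear: SAP 8.2.5 tabulates each concomitant medication and non-drug therapy, and response is split by non-drug therapy. What is missing is the link to response and timing.

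**The shift may be trivial.** With a modest share of patients affected it would lie inside the confidence interval: at a rate of 8%, the exact interval is 6.0% to 10.5% with 600 patients and 5.2% to 11.7% with 300. That is fair, but sampling error and a one-directional bias are different things, and the share affected is unknown.

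**Conclusion.** The point holds as a gap in the visible definition of response. Under SAP 5.2 and 8.2.7 as written, evaluations made during another systemic anticancer drug, or after radiotherapy or surgery for renal cell carcinoma, count toward this drug's response and clinical benefit rates. Concurrent treatment is the main route. The bias has one direction, upward, for a fixed denominator.

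Its size is not known. The documents give neither a response rate nor the share of patients with other anticancer treatment, so the figures above show only what different assumptions would imply. A reader might conclude that the reported rates are materially inflated, or that the plan leaves local treatment unrestricted. The documents establish neither: they record non-drug therapy without saying what is allowed.

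The consequence is for the interpretation of a main effectiveness result. It does not affect the study size or any error rate. The conclusion assumes that the separately specified criteria and the unseen text contain no such rule.

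**What to change.** Keep the all-comers rates and add to SAP 8.2.7 a sensitivity tabulation with these rules:
- Best overall response and clinical benefit use only evaluations dated before the first recorded start of another systemic anticancer drug, or of radiotherapy or surgery given for renal cell carcinoma.
- These treatments are identified from the therapy name, period and reason collected under Protocol 6.3.1 and 6.3.2.
- Patients on a concurrent anticancer drug from Day 1 are shown separately.
- The number of patients affected is reported. The denominators match the main table, and patients left with no qualifying evaluation are counted openly.
- The tabulation states which clinical benefit definition it uses, because SAP 6.2 asks for SD lasting at least 24 weeks and SAP 8.2.7 does not.

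The trigger should be any radiotherapy or surgery for the disease, not treatment of a target lesion, because Protocol 6.3.2 does not collect the treated site. If the separately specified criteria already contain a rule of this kind, citing it in SAP 5.2 and 8.2.7 resolves the point.

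The cost is SAP wording, one derivation and one table from data already collected. The downsides are a second rate that may be lower than the first, and some over-censoring where the treated site was not a measured lesion.
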